2.1 Trial Design

The evaluation follows the MRC framework for complex interventions (17). The study is conducted by a parallel two-armed, pragmatic, superiority cluster-RCTs. Clubs are randomised to either the control group that continue their activity as normal or the intervention group participating in #Utviklingsklar. #Utviklingsklar includes a digital e-learning course, an in-person workshop, and a club meeting, all three activities involving participation of one club leader and a minimum of one coach from each participating team within each club.

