2.3 Sample size

Sample size calculation has been based on the primary endpoint (using player average weekly injury severity score during the study period of one season). Sample size estimations under varying assumptions for cluster size and effect were performed by the project biostatistician. Data from one previous study in the target population were used to estimate the average weekly injury severity score in the control group and expected standard deviation. Assuming club sizes of 64 players, 13 clubs in each trial arm are sufficient to detect a difference between the average weekly injury severity score of 34 (intervention group) and 25.5 (control group), with a pooled standard deviation of 30, 80% power, 2-tailed alpha of 0.05, and an ICC of 0.05 or less. This corresponds to a relative reduction of 25%. We will overshoot recruitment by four clubs to allow for potential withdrawal of clusters. The target number of clubs to recruit is therefore 15 in each trial arm. As cluster sizes are large, the risk of type II errors due to individual participant data loss is minor.

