2.4.2 Decision Rule

This trial is designed to address a single primary outcome. A group difference is claimed if the primary null hypothesis is rejected on the significance level (alpha) of 0.05 (two-sided).

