5.2.1 Primary Outcome

Analysis

The primary outcome (weekly injury severity score) will be analyzed with a linear mixed model. The model will include fixed effects for intervention (intervention vs control), time point, intervention x time point interaction, and geographical region (stratification factor in the randomisation). Time point is defined as 1 for the first response to the OSTRC questionnaire (week 42, 2024), 2 for the second response to the questionnaire (week 44, 2024), and so on until 13 for the last response (week 14, 2025). The model will include random intercepts for players nested within clubs. The predicted margins over all time points will be presented for intervention and control separately with 95% confidence intervals (CIs). The effect measure will be the difference between the weekly injury severity score for intervention and control, estimated as the predicted marginal effect of intervention over all time points, based on the fitted linear mixed model. The effect estimate will be presented with a 95% CI and a P-value for the null hypothesis of a difference equal to zero.

The predicted margins for intervention and control will be presented with 95% CIs for each time point in a plot. The estimated intervention effect (difference between intervention and control) with a 95% CI for each time point will also be shown in a plot.

Assumption checks

The distribution of the primary outcome (injury severity score) will be assessed with descriptive statistics and histograms. With a sample size of approximately 2000, the linear mixed model will be robust to quite large deviations from the normal distribution, and the injury severity score is bounded below at 0 and above at 100, so its distribution cannot be severely skewed. Still, in the unlikely case that the distribution of the outcome is deemed to deviate too much from the normal distribution, a log transformation of the outcome will be done prior to fitting the linear mixed model. In that case, an analysis of the untransformed data will be performed as an additional sensitivity analysis. After fitting the model (original scale or log transformed), plots of observed and model-fitted values (by intervention group and time point) will be compared to assess the fit of the model.

Missing data

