The linear mixed model will handle missing data in one or more time points per player under the assumption of missing at random. No patient in the FAS has missing data on all fourteen time points, per the definition of FAS (see section 3.3).

Subgroup analysis

A subgroup analysis of the primary outcome will be performed by team gender. The analysis will be as described for the primary analysis of the primary outcome above; however, instead of an interaction term between intervention and time point, there will be a three-way interaction between intervention, time point, and team gender. The results will be a separate estimated intervention effect across all time points for each team gender and separate plots of estimated intervention effects for each time point for each team gender. No hypothesis tests for intervention effects will be performed.

STATISTICAL ANALYSIS PLAN for Effectiveness of the Injury-preventive Program #Utviklingsklar

A test for subgroup effect (i.e. a test for the null hypothesis of equal intervention effects for each team gender) will be calculated with a likelihood ratio test for the models with and without interaction by team gender.

Sensitivity analyses

The following sensitivity analyses will be performed for the primary outcome:

- Analysis restricted to the first part of the season (2024, time point 1-6)
- Analysis restricted to the second part of the season (2025, time point 7-14)
- Analysis on untransformed data (only if the primary analysis is done on log-transformed data)

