- Completed coaching courses (coach)
- Satisfaction with injury prevention knowledge in coaching courses (coach)
- Education in health-related field (coach)
- Injury prevention plan (club)
- Participation in injury prevention (Skadefri) club event the last two years (club)
- Employed by club in full-time position (coach)
- Receiving salary for coaching (coach)
- Possessing multiple club roles (coach)
- Number of full-time leaders (club)

STATISTICAL ANALYSIS PLAN for Effectiveness of the Injury-preventive Program #Utviklingsklar

- Member fee (club)
- Age (coach)
- Gender (coach)
- Club
- Region

The number of imputations will equal the percentage of missing values, i.e. 20 imputations for 20% missing data, as per the rule of thumb in (22). In case the imputation model fails to converge, the model will be reduced by one explanatory variable at a time, starting with the last variable listed above and continuing in opposite order as listed.

6. Statistical Software

All statistical analyses will be done in Stata version 17 (StataCorp LLC, College Station, TX, USA).

STATISTICAL ANALYSIS PLAN for Effectiveness of the Injury-preventive Program #Utviklingsklar

7. References

4. Bakken A. Idrettens posisjon i ungdomstida. Hvem deltar og hvem slutter i ungdomsidretten? Oslo: OsloMet - storbyuniversitetet; 2019.
6. Wik EH. Growth, maturation and injuries in high-level youth football (soccer): A mini review. *Frontiers in Sports and Active Living.* 2022;4.

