2.3 Sample size

Sample size calculation has been based on the primary endpoint (using player weekly injury severity score during the study period of one season). Sample size estimations under varying assumptions for cluster size and effect were performed by the project biostatistician. Data from one previous study in the target population were used to estimate the average weekly injury severity score in the control group and expected standard deviation. Assuming club sizes of 64 players, 13 clubs in each trial arm are sufficient to detect a difference between the average weekly injury severity score of 34 (intervention group) and 25.5 (control group), with a pooled standard deviation of 30, 80% power, 2-tailed alpha of 0.05, and an ICC of

STATISTICAL ANALYSIS PLAN for Effectiveness of the Injury-preventive Program #Utviklingsklar

0.05 or less. This corresponds to a relative reduction of 25%. We will overshoot recruitment by four clubs to allow for potential withdrawal of clusters. The target number of clubs to recruit is therefore 15 in each trial arm. As cluster sizes are large, the risk of type II errors due to individual participant data loss is minor.

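### The primary mixed model names neither ML or REML nor a small-sample reference distribution, so with 26 to 30 clubs the one confirmatory test can exceed its 5% level

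*SAP*

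**What the plan says.** The points below read the same in the handball and football SAPs.

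- **Unit of randomisation (2.1):** "Clubs are randomised to either the control group that continue their activity as normal", or to the intervention. Section 2.2 gives a 1:1 ratio, stratified by region.
- **Size (2.3):** "13 clubs in each trial arm are sufficient to detect a difference", assuming "80% power, 2-tailed alpha of 0.05, and an ICC of 0.05 or less". The recruitment target is 15 clubs per arm.
- **Primary model (5.2.1):** "The primary outcome (weekly injury severity score) will be analyzed with a linear mixed model". It has fixed effects for arm, time point, their interaction and region, and random intercepts for club and for player within club. For the season-averaged contrast, "The effect estimate will be presented with a 95% CI and a P-value for the null hypothesis of a difference equal to zero".
- **Decision (2.4.2):** one two-sided test at 0.05.
- **Software (Section 6):** "All statistical analyses will be done in Stata version 17". No command or option is given.

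Two other statements come near the issue without settling it. The large-sample remark in 5.2.1 counts about 2000 players and concerns normality of the outcome, not the number of clubs. The subgroup test is "calculated with a likelihood ratio test for the models with and without interaction by team gender". That comparison involves fixed effects and so needs ML, but the sentence does not say how the primary contrast is fitted.

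**The concern.** Arm varies only between clubs. The precision of the arm contrast is therefore estimated from 26 to 30 club-level units, less the parameters spent on intercept, arm and region. With so few units two choices matter. ML divides the between-club sum of squares by the number of clubs, which biases the variance downwards, whereas REML divides by the degrees of freedom. A normal reference also ignores the uncertainty in that variance, which a t reference allows for.

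The SAP does not prescribe an off-level test, but it permits one. REML with a t reference complies with the text, and so does ML with a normal reference. Because this is the only confirmatory test, the choice could decide whether a group difference is claimed, and it sets how wide the reported CI is. A SAP is the place to fix it.

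**Working it through.** **Inputs.** From 2.3: 64 players per club, SD 30, absolute difference 34 − 25.5 = 8.5, ICC up to 0.05, 13 clubs per arm required and 15 targeted, so G = 26 or 30. From 5.2.1: region as a fixed effect. The number of regions R is not stated; R = 2 to 4 is assumed. Calculations are at player-average level, as in the sample size text, with equal clubs.

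**1. The plan's own figure.** Players per arm = 2 × (1.960 + 0.842)² × 30² / 8.5² = 195.5, rounded up to 196. Design effect = 1 + 63 × 0.05 = 4.15. Clubs per arm = 196 × 4.15 / 64 = 12.7, rounded up to 13. The stated 13 is reproduced, on a normal approximation.

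**2. Degrees of freedom.** Intercept, arm and R − 1 region terms use R + 1 club-level parameters, so df = G − 1 − R: 21 to 23 with 26 clubs and 25 to 27 with 30.

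**3. True level at ICC 0.05.** With equal clubs and a positive club variance estimate, the REML statistic follows t on df, and the ML statistic is that t multiplied by √(G/df). Hence:

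- REML, normal reference: 2 × P(t_df > 1.96)
- ML, normal reference: 2 × P(t_df > 1.96 × √(df/G))

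| Clubs | Regions | df | REML, normal | ML, normal | t critical value |
|---|---|---|---|---|---|
| 26 | 2 | 23 | 6.2% | 7.8% | 2.069 |
| 26 | 3 | 22 | 6.3% | 8.5% | 2.074 |
| 26 | 4 | 21 | 6.3% | 9.3% | 2.080 |
| 30 | 2 | 27 | 6.0% | 7.4% | 2.052 |
| 30 | 3 | 26 | 6.1% | 8.0% | 2.056 |
| 30 | 4 | 25 | 6.1% | 8.6% | 2.060 |

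Coverage of the nominal 95% CI is 100% minus these levels: 93.7-94.0% (REML, normal) and 90.7-92.6% (ML, normal). The t reference widens the CI by 2.052/1.96 to 2.080/1.96, that is 4.7-6.1%, against REML with a normal reference.

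**4. Smaller ICCs.** Here the club variance is sometimes estimated as zero (under REML in 6-8% of draws at ICC 0.01 and about 54% at ICC 0), so the closed form fails. Simulating the between- and within-club sums of squares (400,000 draws per setting, variances truncated at zero) gives:

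| ICC | ML, normal | REML, normal | REML, t |
|---|---|---|---|
| 0.02 | 7.4-9.1% | 6.1-6.3% | about 5.0% |
| 0.01 | 7.0-8.3% | 5.8-6.1% | 4.7-4.9% |
| 0.005 | 6.4-7.2% | about 5.5% | 4.2-4.5% |
| 0 | 4.5-4.8% | 4.1-4.2% | 3.0-3.3% |

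At ICC 0.002, ML with a normal reference gives 5.4-5.8% and REML with a normal reference 4.8-4.9%.

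**5. Unequal clubs.** With 32 to 96 players per club, ICC 0.05 and 3,000 replicates per setting (simulation error 0.4-0.5 points), the levels were 7.3-9.4% (ML, normal), 5.8-6.7% (REML, normal) and 4.7-5.2% (REML, t). A separate run with clubs of 2 to 6 teams of an assumed 16 players, 3 regions and 4,000 replicates gave 7.2-9.2%, 5.5-7.2% and 4.6-5.9%, with simulation error of about 0.4 points.

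**6. Power on a t reference.** SE = √(2 × 900 × DE / (64k)) for k clubs per arm. At k = 13 and ICC 0.05, SE = 2.996 and 8.5/2.996 = 2.837. The normal approximation gives 81.0%. Noncentral t gives 77.7% on 24 df (no region terms), falling to 77.2% on 21 df. With 14 per arm it is 80.5-80.9%, and with 15 it is 83.4-83.7%. At ICC 0.045 (DE = 3.835), 13 per arm give 80.3-80.8%.

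**The case against.** The strongest reply is that this is an omission rather than an error. The model already includes club and player random intercepts, the contrast is defined, and what is missing is a second-order option. The large figures also need an unfavourable combination: ML, a normal reference and an ICC of about 0.01 or more. Their upper ends need four regions; with a single region ML with a normal reference gives 6.9-7.2% at ICC 0.05. Under REML with a normal reference the excess is only 1.0-1.3 points. The SAP gives a ceiling for the ICC, not a value, and near ICC 0 every variant is conservative. The t reference is the most conservative there, at about 3%. Finally, the calculations use player averages and normal errors, whereas the planned model has weekly data with gaps, so tenths of a point should not be read literally.

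All of that is fair as to size. About one point of excess is the milder case and the ML figures are the upper case. None of it closes the gap: the text does not exclude ML, and the SAP's own planning range includes ICCs at which a normal reference exceeds 5%. Blinding the biostatistician guards against a motivated choice but does not correct the level.

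**Conclusion.** The point holds. For the single confirmatory test of an intervention randomised to 26 to 30 clubs, the SAP leaves open an estimator and a reference distribution that together move the true level, at ICC 0.05, from 5.0% (REML, t) to 6.0-6.3% (REML, normal) or 7.4-9.3% (ML, normal). The excess is similar at ICC 0.02 and somewhat smaller at 0.01. At 0.002 it is under 1 point with ML and absent with REML, and at 0 it is absent under both.

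These sizes assume 2 to 4 regions, clubs of 64, and analysis at player-average level. The direction does not depend on the exact number of regions. The matter should be fixed before analysis, but it does not call the design or the recruitment target into question.

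**What to change.** In 5.2.1 of both SAPs, state that the primary model is fitted by REML, and that the season-averaged contrast, its CI and its P-value use one named small-sample method: Kenward-Roger df, Satterthwaite df, or t on clubs minus club-level parameters. One should be chosen in advance, because they can differ when the club variance is estimated at zero. The figures above were computed for the last of the three. Add that ML is used only for the subgroup likelihood ratio test.

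In 2.3, add a short note that at the ICC ceiling of 0.05 a t reference gives about 77-78% power with 13 clubs per arm, that 14 reach 80%, and that the targeted 15 give about 83-84%. At ICC 0.045 or less, 13 per arm still give 80%. No extra clubs are needed.

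The cost is a few sentences in two documents and a CI 4.7-6.1% wider than with REML and a normal reference. Power falls by about 3 points at ICC 0.05, and drops below 80% only if withdrawals leave 13 clubs per arm and the ICC is above about 0.045. With t on clubs minus club-level parameters the test is conservative when the ICC is very small: 4.2-4.5% at 0.005 and about 3% at 0.

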2.4 Statistical Framework

2.4.1 Hypothesis Test

The primary null hypothesis is that there is no difference between #Utviklingsklar and usual practice in the injury severity score in youth handball players over one season. There is only

STATISTICAL ANALYSIS PLAN for Effectiveness of the Injury-preventive Program #Utviklingsklar

one identified primary analysis. All other effectiveness analyses will be regarded as supportive.

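### The log fallback is undefined on the outcomes it is meant for: the severity score includes 0, the coach-practice change includes 0 and negatives, and for the severity score it would become the primary analysis

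*SAP*

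**What the plan says.** The points below stand in both the handball and the football SAP.

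- **Outcome.** Section 5.1.2 builds the severity score from four questions scored 0 to 25, so each total lies between 0 and 100.
- **Effect measure.** Section 5.2.1: "The effect measure will be the difference between the weekly injury severity score for intervention and control". Section 2.3 sizes the trial on that untransformed difference.
- **Trigger.** Section 5.2.1, Assumption checks: "in the unlikely case that the distribution of the outcome is deemed to deviate too much from the normal distribution". No criterion follows.
- **Action.** "a log transformation of the outcome will be done prior to fitting the linear mixed model". No added constant, rule for zeros or back-transformation appears anywhere.
- **Status.** "In that case, an analysis of the untransformed data will be performed as an additional sensitivity analysis". The list of sensitivity analyses confirms it: "Analysis on untransformed data (only if the primary analysis is done on log-transformed data". Section 2.4.1 allows only "one identified primary analysis. All other effectiveness analyses will be regarded as supportive".
- **Reason given for thinking the fallback unlikely.** "the injury severity score is bounded below at 0 and above at 100, so its distribution cannot be severely skewed".
- **Severity-score secondary outcomes.** Section 5.2.2 has them checked in the same way as the primary outcome.
- **Coach practices.** Section 5.2.5 defines change as baseline minus end of season, from -6 to +6, and prescribes a log if the distribution is judged unsuitable. No untransformed sensitivity analysis is listed there.

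**The concern.** The rule prescribes an operation that does not exist for part of the outcome's own range. Whoever runs it must improvise in one of two ways.

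1. **Take the plain log.** Zero scores become missing. The comparison is then restricted to weeks with a positive score, which is a selection made after randomisation. A player who only ever scores 0 leaves the analysis, although section 3.3 places anyone with at least one response in the full analysis set.
2. **Add a constant.** The size of the result then depends on a number that is not fixed in advance.

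For the severity score this is the contingent primary analysis. It would carry the only confirmatory test, on a scale different from the stated effect measure and from the sample size. The choice would be made by judgement after looking at the outcome distribution.

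For coach practices the sign convention makes it worse: the only values with a logarithm are those where practice deteriorated.

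**Working it through.** **Range check**

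| Outcome | Stated range | Is the log defined? |
|---|---|---|
| Severity score (5.1.2) | 0 to 100 | Not at 0 |
| Coach-practice change (5.2.5) | -6 to +6 | Not for -6 to 0, which is 7 of 13 values |
| Behavioural determinant score (5.2.4) | 0.14 to 1.0 | Yes, about -1.95 to 0 |

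A 7-point scale at baseline and at end of season gives 7 × 7 = 49 possible pairs. Of these, 21 are worsened (positive change, log exists), 7 are unchanged and 21 are improved. The last 28 have no log. This counts possible values, not coaches. The determinant scores are unaffected.

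**The plan's own sample size, on the untransformed scale**

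Inputs from section 2.3: means 34 and 25.5, SD 30, 80% power, two-sided 0.05, ICC 0.05, 64 players per club.

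- Per arm without clustering: 2 × (1.960 + 0.842)² × 30² / 8.5² = 195.5, so 196.
- Design effect: 1 + 63 × 0.05 = 4.15.
- Clubs per arm: 196 × 4.15 / 64 = 12.7, so 13.

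The stated 13 reproduces, which confirms that the trial is sized on the mean difference. Below, 34 is read as the usual-practice mean, because 8.5 / 34 = 25% is the relative reduction that the SAP names.

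**Do bounds at 0 and 100 rule out skew?**

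For mean m and SD s on 0-100, skewness can lie between s/m - m/s and (100 - m)/s - s/(100 - m).

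- m = 34, s = 30: 0.882 - 1.133 = -0.25, up to 2.200 - 0.455 = 1.75.
- m = 25.5, s = 30: 1.176 - 0.850 = 0.33, up to 2.483 - 0.403 = 2.08.

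The bounds neither exclude nor establish marked skew. A normal distribution with these values would put Φ(-34/30) = 12.9% or Φ(-25.5/30) = 19.8% below zero, so some departure from normality is certain. How much is too much is not defined.

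**How many zeros are possible?**

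If 30 is the SD of single scores, the largest possible zero share is 1 - m²/(m² + s²): 1 - 1156/2056 = 43.8% at mean 34, and 1 - 650.25/1550.25 = 58.1% at mean 25.5. The smallest is 0. The SAP gives no figure.

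**What each reading would report**

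Assumptions, not from the SAP: zeros 10, 20, 30 or 40% under usual practice; positive scores are integers from 1 to 100 following a beta shape solved so that the overall mean is 34 and the SD 30 (overall skewness 0.57, 0.48, 0.32, -0.01). The ratio is exp(difference in expected log), intervention over control. These are single-observation expectations, not output of the planned mixed model.

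| Way the programme works | Raw mean | Plain log, zeros dropped | log(score + 1) | log(score + 10) |
|---|---|---|---|---|
| (a) 25% fewer injured weeks, random draw | -25% | 1.00 | 0.49-0.55 | 0.74-0.76 |
| (b) Positive scores 25% lower | -25% | 0.75 | 0.79-0.84 | 0.85-0.87 |
| (c) Mildest quarter of positive weeks prevented | -3% to -17% | 1.14-1.85 | 0.58-0.70 | 0.79-0.92 |

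By zero share, (c) under the plain log gives 1.85, 1.63, 1.38 and 1.14, against raw mean ratios of 0.969, 0.947, 0.909 and 0.835. In (a) the plain log returns 1.00 by construction, because the positive scores keep the same distribution.

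**The case against.** The strongest reply is that this is a contingent branch. The default is definite: an untransformed mixed model with one effect measure and one P-value. The SAP calls the branch unlikely and relies on about 2000 players for robustness. If the branch is taken, the untransformed result is still reported. The coach-practice outcomes are only supportive. All of this is true and limits when harm can occur. It does not make the rule executable, and the branch, once taken, holds the primary test.

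Second, the illustrated distributions are only mildly skewed and might not trigger the fallback. That is fair: the ratios show how the log behaves, not what is expected in this trial. The wrong-direction result needs the trigger, dropped zeros and prevention of the mildest weeks together. It also depends on the smallest positive score. With 5 or 8 instead of 1, the 1.85 falls to about 1.6 or 1.5, in the same direction. With an added constant the direction is right in all three scenarios and only the size moves.

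Third, stating a constant, a trigger and an effect scale would also close the gap. It would, but the primary analysis would still move off the effect measure on which the trial was sized.

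Fourth, the argument from bounds and the judgement-based trigger also appear in section 5.2.4. That is correct, but the log exists there, so it is a separate matter.

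**Conclusion.** The fallback is wrong as written in both SAPs and needs to be corrected. This rests on the stated ranges alone: 0 has no logarithm, negative changes have none, and no rule fills the gap. For the severity score the undefined analysis would displace the stated effect measure as the primary analysis, on a trigger without a criterion.

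The size of the harm is conditional. It is nil if the fallback is never used. If it is used, the same 25% fall in the mean could be reported as a ratio anywhere from 0.49 to 1.00, depending on how zeros are handled and how the programme works. The lower and upper ends rest on the assumed zero share and score distribution. Which pattern to expect is not stated: section 1.1 describes both prevention and management of injured players.

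The severity-score secondary outcomes inherit the problem. If players without the relevant injury score 0 on them, which the SAP does not say, they have at least as many zeros as the primary outcome.

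**What to change.** In both SAPs, keep the untransformed mean difference from the stated model as the analysis whatever the distribution. SAP section 5.2.1 already describes that model as robust to sizeable departures from normality.

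- **5.2.1, Assumption checks:** delete the final clause of "the injury severity score is bounded below at 0 and above at 100, so its distribution cannot be severely skewed" (the inference about skewness). Delete the whole sentence containing "in the unlikely case that the distribution of the outcome is deemed to deviate too much from the normal distribution" and the one beginning "In that case, an analysis of the untransformed data will be performed as an additional sensitivity analysis". In the sentence beginning "After fitting the model (original scale or log transformed), plots of observed and model-fitted values", delete the words in brackets.
- **5.2.1, Sensitivity analyses:** delete the item on untransformed data.
- **5.2.5, Assumption checks:** delete the last sentence, which prescribes the log.
- **5.2.2:** no edit of its own, since it refers back to 5.2.1.
- **5.2.4:** not part of this change.

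A bootstrap that resamples clubs may be added as an optional sensitivity analysis. The cost is SAP wording only: no new data and no additional required analysis.
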